### 6.2.2.3 Further secondary efficacy endpoints

- Percentage of participants with a  $\geq 30$  scale units reduction from baseline after 12 weeks of intervention (measured by Cough Severity VAS)
- Percentage of participants with a  $\geq 1.3$ - point increase from baseline after 12 weeks of intervention (measured with LCQ Total Score) [10]

The proportion of participants meeting Cough Severity VAS and LCQ Total Score responder thresholds by intervention group will be compared across intervention groups using a Chi-square test.

Point estimates and CIs for the probability of being a responder will be displayed by intervention group.

### 6.2.3 Exploratory Endpoints

For each exploratory endpoint the following three analyses will be provided:

1. The same estimand as the primary efficacy estimand will be used, in particular the analysis will be on PPS and COVID-19 affected efficacy measurements will be excluded. (The ICes a), b) and c) will be handled as described in Section 6.2.1.)
2. The analysis specified in 1. will be repeated on FAS.
3. The analysis specified in 1. will be repeated on PPS including also all available data during and after potential COVID-19 infection (treatment policy strategy for ICE COVID-19 infection in c) and the ICes a) and b) will be handled as described in Section 6.2.1.)).

#### 6.2.3.1 Exploratory Efficacy Based on Cough Counts

- Change from baseline in night cough frequency per hour after 2, 4, 8, and 12 weeks of intervention (measured by cough recording digital wearable monitoring device)

The exploratory efficacy endpoints of night cough count at different time points will be analyzed similar to the secondary efficacy endpoint of awake cough count at different time points.

- Percentage of participants with a  $\geq 50\%$  and  $\geq 70\%$  reduction from baseline in 24-hour cough count after 12 weeks of intervention

The proportion of participants meeting the responder threshold will be compared across intervention groups using a Chi-square test.

Point estimates and CIs for the probability of being a responder will be displayed by intervention group.

#### 6.2.3.2 HRQoL and PRO Associated Exploratory Endpoints

- Change from baseline in cough severity after 2, 4, and 8 weeks of intervention (measured by Cough Severity VAS)

- Change from baseline in cough related quality of life after 2, 4, and 8 weeks of intervention (measured by LCQ) [each domain as well as the total score]

Summary statistics (arithmetic mean, SD, minimum, median, quartiles and maximum) and difference to baseline will be provided for the LCQ and VAS by treatment.

As exploratory endpoint the change in Cough Severity VAS and LCQ from baseline to Week 2, Week 4 and Week 8 will be analyzed with the same repeated measurement model as the secondary efficacy endpoint.

- Change from baseline in daily cough severity after 2, 4, 8, and 12 weeks of intervention (measured by the individual items of the Severity of Chronic Cough Diary [SCCD])
- Patient Global Impression of Change (PGI-C) and change from baseline in Patient Global Impression of Severity (PGI-S), after 2, 4, 8 and 12 weeks of intervention.

SCCD (individual items), PGI-C and PGI-S will be summarized by minimum, median, quartiles and maximum.

Frequency tables providing the number and percentages of the different response options to individual questions will be displayed for PGI-S and PGI-C.

In addition, changes from baseline for the single questions will be displayed.

These summary statistics and difference to baseline will be presented by treatment.

- Change from baseline in Health-related quality of Life (HrQoL) after 2, 4, 8 and 12 weeks of intervention (as measured by EQ-5D-5L)

Descriptive assessment will be done on the basis of the VAS and on dimension level assessment basis.

Frequency tables providing the number and percentages of the different response options to individual questions will be displayed. In addition, changes from baseline for the single questions will be displayed by treatment.

The EQ visual analogue scale (VAS) values of the EQ-5D-5L and their changes to baseline will be summarized by treatment as continuous variable; arithmetic mean, SD, minimum, quartiles, median and maximum will be displayed by treatment.

The scoring algorithm described in the EQ-5D-5L manual [11] will be used.

### 6.2.3.3 Further exploratory efficacy endpoints

- Sleep disturbance (prevalence and impact) associated with cough in patients with RUCC

For the endpoint of sleep disturbance question 12 and 13 of SCCD will be assessed.

The following scores for the verbal rating answers will be used:

- 0 = “No cough”,
- 0 = “Not at all”,
- 1 = “A little”,

- 2 = “Some”,
- 3 = “A lot”,
- 4 = “Could not sleep”

The total score will be the average of the individual scores of question 12 and 13. A flag variable will be added so that it is possible to go back and distinguish which 0-responses were originally ‘No cough’ and which ‘Not at all’.

- Frequency of urinary incontinence associated with cough in patients with RUCC. This endpoint will be based on question 14 of SCCD.

#### 6.2.4 Subgroup Analyses

The primary analysis of the primary and secondary endpoints will be repeated for the following subgroups:

- Duration of cough (since the start of Chronic Cough in years) (<10 years, ≥ 10 years)
- Baseline 24-hour coughs per hour
  - <10 coughs/hr, ≥10 coughs/hr
  - <20 coughs/hr, ≥20 coughs/hr
  - <30 coughs/hr, ≥30 coughs/hr
- Baseline awake coughs per hour (<20 coughs/hr, ≥20 coughs/hr)
- Baseline Cough Severity VAS (<60 mm, ≥60 mm)
- FEV1/FVC ratio (60 to <70, ≥70)
- Primary diagnosis: Unexplained Chronic Cough vs Refractory Chronic Cough
  - Patients with MHTERM = “Unexplained Chronic Cough” and MHOCCURN = “NO” will be assigned to the subgroup “Refractory Chronic Cough”.
  - Patients with MHTERM = “Unexplained Chronic Cough” and MHOCCURN = “YES” will be assigned to the subgroup “Unexplained Chronic Cough”.
- Standard Subgroups
  - Age (<60 years vs. ≥60 years; <65 years vs. ≥65 years)
  - Sex (male vs. female)
  - Race (white, black, Asian, other)
  - BMI (< 30 kg/m^2, ≥ 30 kg/m^2)
  - Weight (<60, 60 to <90, ≥90 kg)
  - Region:
    - Asia - Japan and Taiwan
    - Europe - Belgium, Czech Republic, France, Germany, Hungary, Italy, Netherlands, Poland, Slovakia, Spain, United Kingdom
    - Pacific - Australia
    - North America - United States and Canada
    - ROW - Argentina, Russian Federation, Turkey
- eGFR category at baseline (eGFR < 60 and ≥ 60 mL/min/1.73m^2)
- Smoking status:
  - Never

- Stopped smoking  $\geq 10$  years ago
- Stopped smoking 3 to  $< 10$  years ago
- Stopped smoking  $< 3$  years ago
  
- Background medication (medications taken at least once during the study):
  - azithromycin/erythromycin use the following ATC codes at the same time:
    - D06AX, D10AF, J01FA, S01AA (azithromycin)
    - D10AF, J01FA, S01AA (erythromycin)
  - gabapentin/pregabalin: use the following ATC codes at the same time
    - N02BG, N03AX, N07XX (gabapentin)
    - N02BG, N03AX, N05BX (pregabalin)
  - antihistamines with chronic cough indication: use the SDG "Antihistamines and antiallergics" and the indication
  - tricyclic antidepressants use all ATC codes for amitriptyline and amitriptyline hydrochloride at the same time (other tricyclic antidepressants are not relevant): G04BD, N02BG, N02CX, N05BX, N06AA
  - asthma medications: use the SDG "Drugs for obstructive airway diseases"
  - proton-pump inhibitors: use the SDG "Proton-pump inhibitors"
- Previous treatment with a P2X3 receptor antagonist in the last three months (no vs. yes)
- Time of randomization ("Patients randomized up to and including the day the first 236 patients were randomized" vs. "Patients randomized after the day the first 236 patients were randomized")

The primary analysis of the primary efficacy will only be conducted for subgroups consisting of at least 5 participants. The MMRM for the HRQoL and PRO associated secondary endpoints will only be applied for subgroups consisting of at least 5 participants.

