6.5 Prior and Concomitant Therapy

Any medication or vaccine (including over-the-counter or prescription medicines, vitamins, and/or herbal supplements) that the participant is receiving at the time of enrollment up to 12 weeks prior to screening or receives during the study must be recorded along with:

- Reason for use
- Dates of administration including start and end dates
- Dosage information including dose and frequency

The Medical Monitor should be contacted if there are any questions regarding concomitant or prior therapy.

A list of prohibited prior and concomitant medications, along with the timeframe is provided in [Table 6–2](#).

Medications that are allowed only if the participant is on stable treatment (prior to and at enrollment) are described in [Table 6–3](#). Other treatment considerations are described below.

Table 6–2: Prohibited Prior and Concomitant Therapy

Therapy	Timeframe
Angiotensin converting enzyme inhibitor (ACEI)	From 12 weeks prior to screening until EoI
Opioids, including codeine	From 2 weeks prior to screening until EoI
Digoxin	From 2 weeks prior to screening until 2 weeks after EoI
Dabigatran	From 2 weeks prior to screening until 2 weeks after EoI
Apixaban	From 2 weeks prior to screening until 2 weeks after EoI
Edoxaban	From 2 weeks prior to screening until 2 weeks after EoI
Gabapentin/pregabalin (for chronic cough)	From 2 weeks prior to screening until EoI
Tricyclic antidepressants (i.e., amitriptyline, nortriptyline) (indication RUCC)	From 4 weeks prior to screening until EoI
Interferon alpha-2b and alpha-2a	From 2 weeks prior to screening until EoI
Mycophenolate mofetil	From 1 week prior to screening until EoI
Methotrexate	From 4 weeks prior to screening until EoI
Ribavirin	From 2 weeks prior to screening until EoI
Non-narcotic cough medicine (including over-the-counter and herbal)	From 1 week prior to screening until EoI
Strong cytochrome P450 isoenzyme 3A4 (CYP3A4) inhibitors including: 
 • antivirals (e.g., viekira pak, telaprevir, boceprevir), • protease inhibitors (e.g., ritonavir, lopinavir, indinavir, nelfinavir, saquinavir) • antifungals (e.g., itraconazole, voriconazole, posaconazole) • antibiotics (e.g., clarithromycin, telithromycin) 	From 2 weeks prior to screening until EoI
grapefruit and any grapefruit containing food products (e.g., grapefruit juice)	

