Strong CYP3A4 inducers, e.g., rifampicin, carbamazepine, phenytoin, St John's Wort	From 2 weeks prior to screening until EoI
Non-drug treatment for RUCC	
Speech Therapy	From 4 weeks prior to screening until EoI
Chinese medicine	From 4 weeks prior to screening until EoI

Abbreviations: EoI = end of intervention; RUCC = refractory and/or unexplained chronic cough

A list of permitted medication only on stable dose is provided in [Table 6–3](#). It is not permitted to change the daily dose of these medications within the timeframe described below (prior to and screening).

Table 6–3: Medication Permitted on Stable Dose

Therapy	Timeframe of stable treatment
Benzodiazepines	From 4 weeks prior to screening until Eol
Paroxetine	From 4 weeks prior to screening until Eol
Baclofen	From 4 weeks prior to screening until Eol
Memantine	From 4 weeks prior to screening until Eol
Azithromycin and erythromycin	From 4 weeks prior to screening until Eol
Antihistamines (Chlorphenamine) for chronic cough	From 4 weeks prior to screening until Eol
Gabapentin/pregabalin (other indications e.g., diabetic neuropathy, neuropathic pain)	From 4 weeks prior to screening until Eol
Tricyclic antidepressants (i.e., amitriptyline, nortriptyline) (other indications)	From 4 weeks prior to screening until Eol
Asthma medications (e.g., inhaled corticosteroids, leukotriene modifiers, long-acting beta agonists, theophylline)	From 4 weeks prior to screening until Eol
Proton-pump inhibitors	From 8 weeks prior to screening until Eol

Abbreviations: Eol = end of intervention

Dose changes in these medications should be avoided during the study. Dose changes considered clinically necessary by the investigator need to be documented in the eCRF and the clinical condition / diagnosis that led to this dose modification should be captured as AE.

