Occasional intake of proton-pump inhibitors as treatment for concomitant AE, at the discretion of the investigator is allowed, but not recommended. Alternative treatment options are strongly suggested to be considered.

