### 6.1.4 Prior and Concomitant Medications

The number of participants that used prior and concomitant medication will be analyzed using frequency tables based on classified data. The classification will be done according to the WHO-DD. All prior and concomitant medications will be listed separately. The tables will display the following three categories: prior, prior/concomitant and post-treatment.

Regarding medication data collected during the study course, the following rules will be implemented:

- If the stop time of medication is before the time of the first study drug administration then medication is considered to be **prior** medication.
- If the start time of medication is before or at the time of the first study drug administration and the stop time of medication is after or at the time of the first study drug administration then the medication is considered to be **concomitant** medication.
- If the start time of medication is at or after the time of the first study drug administration and earlier than 14 days after or at the time of the last study drug administration then the medication is considered to be **concomitant** medication.
- If the start time of medication is later than 14 days after the time of the last study drug administration then the medication is considered to be **post-treatment** medication.

If time information is missing but only date information is given then classification of medication as prior or concomitant will be done by date information only. In such case, if the start day of medication is the same date as the first study drug administration, then the medication will be classified as concomitant medication.

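### The background-medication subgroups in SAP 6.2.4 count any use during the study, so participants who first take the drug after randomisation can be mixed with stable baseline users

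*SAP*

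**What the plan says.** SAP 6.2.4 repeats the primary analysis of the primary and secondary endpoints in a long list of subgroups. One item is "Background medication (medications taken at least once during the study"). It covers six classes: azithromycin/erythromycin, gabapentin/pregabalin, antihistamines for chronic cough, tricyclic antidepressants, asthma medication and PPIs. Users are found by ATC code, for example "D06AX, D10AF, J01FA, S01AA (azithromycin"), or by a standard drug grouping. Only the antihistamines carry an indication filter, and none of the six carries a start date. Other items in the list, such as cough rate, VAS and eGFR, are fixed at baseline.

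SAP 6.1.4 has two timing rules that bear on this. One begins "If the start time of medication is before or at the time of the first study drug administration and the stop time" and picks out drugs in use at first dose. The other begins "If the start time of medication is at or after the time of the first study drug administration" and picks up drugs started later, until 14 days after the last dose. Both lead to the same label, concomitant. Section 6.2.4 refers to neither.

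Protocol 6.5 introduces the Table 6–3 list as "Medications that are allowed only if the participant is on stable treatment (prior to and at enrollment"). Protocol 6.5.1 adds an exception: "Occasional intake of proton-pump inhibitors as treatment for concomitant AE, at the discretion of the investigator is allowed", though it is not recommended.

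**The concern.** A subgroup supports a randomised comparison when membership is settled before treatment can influence it. Here membership can be settled later, by an event that may be related to the arm or to the outcome. A participant who takes a PPI once for an adverse event in Week 6 becomes a background PPI user. So, read literally, does one who starts a listed drug during safety follow-up.

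Two things are at stake. If starts depend on how cough evolves on treatment, the user and non-user contrasts can differ where no true difference exists. Even if starts are unrelated to arm, the user group no longer answers the question its label suggests, namely whether the drug works in people who enter on that medication. Without a cut-off, membership could also change between the primary completion analysis and the final analysis described in SAP Section 3.

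**Working it through.** **Step 1: who can enter a user group after randomisation.**

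| Class | Start during treatment | Start after end of intervention |
|---|---|---|
| PPIs | Allowed occasionally for an adverse event (Protocol 6.5.1) | Table 6–3 limit has ended |
| Macrolides, asthma drugs, antihistamines for cough | Departs from the stable-treatment condition (Table 6–3) | Table 6–3 limit has ended |
| Gabapentinoids, tricyclics | For cough: prohibited (Table 6–2). Other indications: departs from Table 6–3 | Both limits have ended |

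The Schedule of Activities collects medication up to the safety follow-up visit, so later starts are in the data. If the programmer read the definition as concomitant medication under SAP 6.1.4, starts in the first 14 days after the last dose would still count.

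**Step 2: size.** The plan gives no start rates and no figure on this point, so size can only be illustrated. Plan inputs (Protocol 9.2): maximum effect −0.35, placebo change −0.19, SD 0.8, 50 evaluable per group. As a check on these inputs, a maximum-contrast test with the four candidate models gives power of 84.7% to 91.4%, against the stated minimum of 85%.

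*Simulation.* Assumed: 5%, 10% or 20% are baseline users, and the true effect is −0.35 in everyone. Three mechanisms for new starts were tried:
- Infection: 10% in each arm are infected, cough rises by 0.5, and half of them start the drug.
- Mild dependence on cough: log-odds of starting = −3 + 0.5 × (change + 0.19)/0.8. This is a 4.7% start rate at the placebo mean and an odds ratio of e^0.5 = 1.65 per SD.
- Strong dependence: slope 1.0, odds ratio e^1 = 2.72 per SD.

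| Mechanism | Baseline users | Difference, users | Difference, non-users | Gap |
|---|---|---|---|---|
| Infection | 5 / 10 / 20% | −0.350 / −0.352 / −0.350 | −0.350 / −0.350 / −0.350 | about 0 |
| Mild | 5 / 10 / 20% | −0.366 / −0.366 / −0.363 | −0.347 / −0.348 / −0.346 | 0.019 / 0.018 / 0.017 |
| Strong | 5 / 10 / 20% | −0.396 / −0.397 / −0.387 | −0.334 / −0.333 / −0.334 | 0.062 / 0.064 / 0.053 |

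Grouping by baseline use alone gave about −0.35 in every scenario. Under the infection mechanism the contrast survives, but starters make up 17% to 49% of the placebo user group. The mean change among placebo users moves from −0.19 to between −0.06 and +0.08.

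*Hand-worked case.* Assume a share p of baseline non-users start (12% placebo, 6% active), starters do g = 0.4 worse than non-starters, and a share b are baseline users.
- Non-user mean shifts by −p·g: placebo −0.048, active −0.024. The effect there shrinks by 0.024.
- User mean shifts by [p(1−b)/(b+p(1−b))]·g(1−p). At b = 20%: placebo (0.096/0.296) × 0.352 = 0.114; active (0.048/0.248) × 0.376 = 0.073. The effect there grows by 0.041.
- The gap is 0.024 + 0.041 = 0.065. At b = 10% the user term is 0.051 (gap 0.075); at b = 50% it is 0.016 (gap 0.040).
- The user term exceeds 0.024 only when b is below about 38%.
- With equal p in both arms, all of these distortions of the contrast vanish.

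**Step 3: against sampling error.** With 50 per arm and 20% users, one dose against placebo has standard error 0.8·√(2/10) = 0.358 in users and 0.8·√(2/40) = 0.179 in non-users. The standard error of the gap is √(0.128 + 0.032) = 0.40. A gap of 0.06 is 15% of that.

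**The case against.** The best defence is that the protocol already makes most users baseline users. The listed drugs are allowed only on stable treatment from 4 weeks (PPIs: 8 weeks) before screening until end of intervention. Gabapentinoids and tricyclics for cough are prohibited over the treatment period, and exclusion criterion 16 bars anyone intending to start new treatment for the condition. Some participants who depart from these rules may leave the per-protocol set; the criteria are in the ACIR, which is not among the documents. The SAP also states its own meaning for the term, and it sets no decision rule on any subgroup.

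Most of this stands, and it rules out stronger readings:
- A reader might infer that new starters make up or dominate these subgroups. The documents do not show that; starters are an admixture of unknown size.
- A reader might infer that on-treatment starts are equally open in all six classes. Only PPIs have a documented permission.
- The protocol sentence "Dose changes considered clinically necessary by the investigator need to be documented in the eCRF" might be taken as evidence of new starts. It concerns drugs already in use, and a dose change does not turn a non-user into a user.
- A reader might infer that the treatment contrast must be biased in both groups, and always more in users. Balanced starts leave it intact, and the hand-worked case shows the second part depends on baseline use.

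What the defence does not cover is the permitted PPI start, the starts after end of intervention, and the absence of any start-date condition.

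**Conclusion.** The point holds as a minor one. The definition lets events after randomisation decide membership, and the documents provide for at least two such routes.

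If starts depend on on-treatment cough, the spurious gap between users and non-users is modest: about 0.02 to 0.06 log units in the simulation, at most 0.06/0.35 = 17% of the assumed maximum effect. The hand-worked case gives 0.04 to 0.075, because it assumes that placebo participants start at twice the active rate. All of these figures rest on assumed start rates and baseline use; none can be derived from the documents. Against sampling error in subgroups of this size they are small. If starts are balanced across arms, the loss is one of interpretation rather than bias in the contrast.

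It would be wrong to infer that the dose-response test is at risk. The primary analysis, its error rate and the sample size do not use these subgroups.

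**What to change.** In SAP 6.2.4, define the six subgroups by medication ongoing at first study drug intake: started before or at the first dose and not stopped before it. SAP 6.1.4 already words this rule, so a cross-reference is enough. List drugs first taken after that point separately, split into on-treatment and later starts.

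The cost is one derivation rule on dates already collected. Two details come with it. A convention is needed for partial start dates, because SAP 4.3.1.2 settles only whether a drug is concomitant, not whether it was in use at first dose. Some user subgroups will also become smaller; the five-participant minimum in SAP 6.2.4 already covers those that become too small for the primary-endpoint analysis and the mixed models.

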9.2 Sample Size Determination

Sample size calculations were performed for establishing evidence of a drug effect across the doses, that is, detecting a statistically significant dose response signal for the primary efficacy outcome in this study using the MCP-Mod approach.

Treatment effects are here presented on the log scale of average hourly counts, measured over 24 hours (see Section 9.4.2 for calculation details and interpretation).

Assuming a true change in cough count under placebo after 12 weeks of -0.19 (17% reduction), a maximum cough count change of -0.35 for BAY 1817080 over placebo (30%

reduction relative to placebo), a common standard deviation of 0.8, a set of plausible dose-response shapes including Emax and sigmoidal Emax models (chosen based on BAY 1817080 effects in Study 18184 combined with literature review), random allocation of participants to dose groups according to a 1:1:1:1 ratio, a sample size of 50 participants per dose groups will have at least 85% power to demonstrate a dose-response relationship, using a one-sided test at a type I error rate of $\alpha=0.10$. Approximately 236 participants will be randomized to achieve 200 evaluable participants for an estimated total of 50 evaluable participants per intervention group. The number of participants to be randomized might be increased if more participants than expected become unevaluable due to COVID-19 related circumstances, to maintain the goal of 50 evaluable participants per intervention group.

With this sample size, the dose-response curve is expected to be estimated with 80% confidence bands of half-widths of 0.14 to 0.16, depending on the underlying dose-response relationship.

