### Analysis

In a first step the mean parameter estimates from an ANCOVA model and the corresponding covariance matrix are obtained. After this step, these two parameters will then be used during the rest of the MCP-Mod procedure.

For the estimation of  $\hat{\mu}$  and  $\hat{\mathcal{S}}$  in the initial stage SAS will be used. All MCP-Mod steps will be performed using the R “DoseFinding” package (version 0.9-17 or higher) [7].

Step 1: Estimation of  $\boldsymbol{\mu}$  and  $\mathbf{S}$  from ANCOVA model with covariate adjustment

An ANCOVA model, following adjustment for baseline cough count and region via the inclusion of covariates  $z$ , will be used to estimate the expected dose response  $\mu_{d_k}$  in each dose group  $k$ .

For participant  $i$  the response is then defined by:

$$Y_{ki} = \beta_0 + z_{1ki}\beta_1 + z_{2ki}\beta_2 + \mu_{d_k} + \varepsilon_{ki}$$

where  $\varepsilon_{ki} \sim \mathcal{N}(0, \sigma^2)$ ,  $k = 1, \dots, K$  and  $i = 1, \dots, n_k$ .

Let  $\hat{\boldsymbol{\mu}}$  denote the vector of estimated dose-response and let  $\mathbf{S}$  denote the variance-covariance of  $\hat{\boldsymbol{\mu}}$ . The estimate of the covariance matrix  $\mathbf{S}$  will be denoted by  $\hat{\mathbf{S}}$ .

Step 2: Detection of dose-response signal

For detecting an overall trend, or a dose-response signal, each of the  $M=4$  dose-response shapes in the candidate set will be tested, using a single contrast test.

For each model  $m$  in the candidate set

the null hypothesis  $H_{0m}: (\mathbf{c}_m)' \boldsymbol{\mu} = 0$

will be tested against

the respective 1-sided alternative hypothesis,  $H_{1m}: (\mathbf{c}_m)' \boldsymbol{\mu} > 0$

where  $\mathbf{c}_m = (c_{m1}, \dots, c_{mK})'$  is the optimal contrast vector representing model  $m$ . The contrast coefficients for the  $m$ -th model are chosen such that they maximize the power for a single candidate model shape

$$\boldsymbol{\mu}_m^0 = (\mu_{m1}^0, \dots, \mu_{mK}^0)' = (f_m^0(d_1, \boldsymbol{\theta}_m^0), \dots, f_m^0(d_K, \boldsymbol{\theta}_m^0))',$$

where  $f^0$  is the standardized version of the dose-response model

$$f(d, \boldsymbol{\theta}) = \theta_0 + \theta_1 f^0(d, \boldsymbol{\theta}^0).$$

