### 6.2.2.2 HRQoL and PRO Associated Secondary Endpoints

- Change from baseline in cough related quality of life (measured by Leicester Cough Questionnaire (LCQ)) after 12 weeks of intervention.

The scoring algorithm described in the LCQ manual [9] will be used.

The analysis will be the change in LCQ (each domain as well as the total score) from baseline to week 12 using mixed model repeated measures (MMRM). This method will assume that any missing data is Missing at Random (MAR).

The model statement is:

$$\Delta Y_{jtkl} = Y_{j0} + \mu_0 + trt_k + visit_t + (trt * visit)_{kt} + region_l + P_j + \varepsilon_{jtkl},$$

where  $\Delta Y_{jtkl}$  is the change from baseline to visit  $t$  for subject  $j$  within treatment group  $k$  and region  $l$ .

- $\mu_0$  is the intercept
  - $Y_{j0}$  is the baseline covariate effect
  - $trt_k$  is the fixed effect of treatment group  $k$
  - $visit_t$  is the fixed effect visit  $t$
  - $(trt*visit)_{kt}$  is the interaction fixed effect of treatment  $k$  by visit  $t$
  - $Region_l$  is the fixed effect of stratification factor
  - $P_j$  is the patient specific random effect.
- $P$  and  $\varepsilon_{tkl}$  will be assumed as normally distributed random variables.

Correlations among measurements taken on the same patient will be modelled with an unstructured covariance assumption. The degrees of freedom will be computed according to the method detailed by Kenward and Roger.

For each active dose  $d_k$  the null hypothesis:

$$H_{0k}: \mu_1 = \mu_k$$

will be tested against the alternative hypothesis

$$H_{1k}: \mu_1 \neq \mu_k$$

within this model.

Least square mean estimates, estimates of treatment differences and corresponding confidence intervals (CIs) will be computed. The least square mean estimates of treatment difference at week 12 are the main estimates of interest; however, differences at all other visits and overall treatment differences (averaged across all visits) will also be estimated as exploratory endpoints.

The core SAS-code to be used is the following (variable and dataset names are for illustration only and may be subject to change):

```
proc mixed data=adqslcq;
  class subject treat visit region;
  model change = base treat visit region treat*visit /ddfm=KR;
  repeated visit / subject=subject type=un group=treat;
  lsmeans treat*visit /cl diff;
  ODS OUTPUT TESTS3=TYPE3 LSMMeans=LSMEAN ESTIMATES=ESTIM;
run;
```

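### Subgroup MCP-Mod and MMRM analyses may run on 5 participants in total, too few for either model, and nothing in the section estimates whether effects differ between subgroups

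*SAP*

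**What the plan says.** SAP 6.2.4 opens with "The primary analysis of the primary and secondary endpoints will be repeated for the following subgroups" and lists the factors, including six classes under "Background medication (medications taken at least once during the study"). Its only size rules are "The primary analysis of the primary efficacy will only be conducted for subgroups consisting of at least 5 participants" and "The MMRM for the HRQoL and PRO associated secondary endpoints will only be applied for subgroups consisting of at least 5 participants". It gives no per-arm minimum, treatment-by-subgroup interaction, reduced model for small levels, multiplicity rule across subgroups, or statement that the results are exploratory.

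The models repeated in each level are those of the main analysis. SAP 6.2.1.1 Step 1 is an ANCOVA, "following adjustment for baseline cough count and region via the inclusion of covariates". SAP 6.2.2.2 is an MMRM coded with "repeated visit / subject=subject type=un group=treat", followed by a sequence of simpler covariance structures if the fit fails. The statement in SAP 6.2.1.1 that multiplicity is taken care of concerns the four candidate contrasts within one analysis.

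**The concern.** A size rule should screen out subgroups in which the model cannot be fitted or its error rate cannot be trusted. A floor of 5 in total does neither: it is no larger than the smallest possible number of mean parameters, and an arm may be empty. Just above the floor the model runs on one to a few residual degrees of freedom.

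A separate issue affects large subgroups too. A dose-response verdict in each level invites the reader to compare one significant level with a non-significant one, which does not test whether the effects differ. Readers planning Phase 3 could draw wrong conclusions about populations from such tables.

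**Working it through.** **1. The plan's own figure.** Inputs from Protocol 9.2 and Table 9–1: 50 per arm, SD 0.8, one-sided alpha 0.10, four candidate models. The maximum-contrast test was simulated 300,000 times with optimal contrasts and critical value 1.479 (multivariate t, 196 df). Power is 84.6% (Emax1), 85.2% (Emax2), 89.1% (sigmoidal Emax1) and 91.3% (sigmoidal Emax2). The plan says the design "will have at least 85% power to demonstrate a dose-response relationship", so the figure reproduces to within rounding.

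**2. ANCOVA at n = 5.** Mean parameters: 4 arms + 1 baseline + 2 for region (three levels, SAP 4.5.7) = 7, or 5 if only one region is present. Residual df: 5 − 7 = −2, or 5 − 5 = 0. The residual variance, and so the covariance matrix of the arm estimates, cannot be obtained. With equal allocation, all four arms are present with probability 240/1024 = 23.4%.

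**3. MMRM at n = 5, all four arms present.** Fixed effects: intercept 1 + baseline 1 + treatment 3 + visit 3 + region 2 + treatment-by-visit 9 = 19, on at most 5 × 4 = 20 observations. The first covariance structure has 4 × 5/2 = 10 parameters per arm, 40 in all. The fallback reduces this to 10, 5 or 2. The fallback leaves the mean model as it is, and 7 fixed effects vary between participants (1 + 1 + 3 + 2; 5 with one region). Five participants leave no between-participant degrees of freedom.

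**4. Error rate where the ANCOVA can be fitted.** ANCOVA plus generalised MCP-Mod was simulated under no effect, with normal critical value 1.478 and redundant region terms dropped. Assumed, not in the documents: region shares of 15/55/30%. There were 3,000 runs per size (1,500 at n = 100). The simulation error on the rate is about 1 point at n = 8 and less at the other sizes.

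| Subgroup n | All arms present (exact) | Fitted | False positive among fitted |
|---|---|---|---|
| 5 | 23.4% | 0% | none |
| 8 | 62.3% | 57.5% | 22.2% |
| 10 | 78.1% | 78.0% | 15.1% |
| 12 | 87.5% | 86.9% | 13.6% |
| 20 | 98.7% | 98.9% | 11.6% |
| 100 | not computed | 100% | 9.5% |

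A repeat gave 23%, 15%, 14% and 11% at n = 8, 10, 12 and 20. Other runs gave 18 to 21% at n = 8 and 13 to 16% at n = 10.

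**5. Number of levels.** Duration 2, 24-hour cough 6, awake cough 2, VAS 2, FEV1/FVC 2, diagnosis 2, age 4, sex 2, race 4, BMI 2, weight 3, region 5, eGFR 2, smoking 4, medication 12 (six classes, yes/no), prior P2X3 antagonist 2, time of randomization 2: total 58. With medication users only, 58 − 6 = 52. Under no effect anywhere, the expected number of false signals on the primary endpoint is 58 × 0.10 = 5.8, or 52 × 0.10 = 5.2.

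**6. Disagreement when the true effect is the same in everyone.** A half-size subgroup (25 per arm) has power p of 63.1 to 71.7%, depending on the model. Two halves disagree with probability 2p(1 − p): 2 × 0.631 × 0.369 = 46.6%, and 2 × 0.717 × 0.283 = 40.6%. Direct simulation under Emax2 gave 45% for a 100/100 split and 63% for 170/30.

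**The case against.** The strongest reply is that the floor permits an analysis without promising a result. At n = 5 the outcome is an empty table, so a reader who infers that 5 participants could yield a false signal goes too far. That objection stands. At n = 6 a fit is also rare: about 2% in the run above, about 7% in another, and 39% only if region is dropped altogether.

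The false-positive rates are conditional on a fit. Over all subgroups of 8 the rate is 0.575 × 22.2% = 12.8%, and at n = 10 it is 0.780 × 15.1% = 11.8%. A printed table is by definition a fitted one, however, so the conditional rate is the relevant one for its reader. The normal reference is inferred from the distributional assumption in SAP 6.2.1.1. Step 2 names only a multiplicity-adjusted critical value.

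It is tempting to read 58 independent tests into the section, with a 1 − 0.9^58 = 99.8% chance of some false signal. The levels overlap, and a simulation with assumed subgroup prevalences gave about 87%. Some levels will barely exist: exclusion criterion 27 should nearly empty the recent-P2X3 group. The 5.8 false signals and the 41 to 47% disagreement also belong to different truths (no effect, and a uniform effect) and must not be added together.

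Finally, no decision rule uses subgroups. SAP 6.2.1.1 Step 3 bases the target dose on primary, secondary and other efficacy variables and on safety. This stands and limits the point to interpretation.

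**Conclusion.** The floor of 5 in total is too low for both models. At the floor nothing can be estimated for four arms. At about 8 to 12 participants, fitted models give false signals at about 14 to 23% instead of 10%, and by 20 participants the excess is 1 to 2 points. These rates rest on a normal reference, the assumed region mix and a rule for dropping redundant region terms that the SAP does not contain.

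In larger subgroups the weakness is the missing estimate of difference: a uniform effect leaves two equal halves in disagreement in about 41 to 47% of trials. That figure takes the Protocol's effect and SD as true.

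A reader might infer that the trial's type I error or its dose selection is compromised. The documents do not support that, because the primary test is run once on the full PPS and no subgroup result enters a stated decision. This is worth correcting, but it is not a flaw in the main conclusion.

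**What to change.** In SAP 6.2.4:

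- Replace the total minimum by a per-arm minimum, for example at least 5 PPS participants in each of the four arms, with descriptive summaries below it. This leaves 20 − 7 = 13 residual df in the full ANCOVA. It secures a fit but not power, which would be only 28 to 32% at 5 per arm.
- State that the region covariate is dropped where it is constant or has empty levels. It is constant in four of the five geographic subgroups (Europe, Pacific, North America, ROW), because each lies within one randomization stratum.
- In place of a dose-response verdict per level, show differences from placebo with confidence intervals, plus a treatment-by-subgroup interaction estimate with its interval from the full PPS. An interval is preferable to an interaction p value, since about 25 such p values would form a new set of uncontrolled tests.
- Label the results exploratory.

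Critical values from the t distribution with the residual df are optional once the floor is set. The cost is SAP wording and the loss of some small tables. The data are already collected. The interaction estimates will be imprecise with about 200 evaluable participants.
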